The purpose of this study is to investigate the efficacy of the vaccines as a booster dose for COVID-19 in solid organ transplant recipients. The aims and objectives of this study is to check the immunogenicity after booster dosing of adenovirus vector vs. mRNA vaccine as a third dose. We are also going to investigate the safety of the third dosing after completion of two doses of mRNA vaccine.

Hypothesis of this study:

Booster dosing with mRNA vaccine should result in a higher rate of immunogenicity, defined as positive IgG, as compared to Adenovirus vector vaccine in solid organ transplant recipients who completed two doses of mRNA vaccine series.

2) **Background***

Severe acute respiratory syndrome coronavirus 2 (SARS-CoV-2), the etiology behind the coronavirus disease 2019 (COVID-19) worldwide pandemic, has resulted in significant mortality rates worldwide. Among immunocompromised hosts, such as solid organ transplant (SOT) recipients, several reports have indicated a significantly higher hospital admission rate and mortality^{1,2}; hence the need to provide robust protection in this vulnerable population.

IRB Study Number: 20210641
Version #4, Date: October 26, 2021

Since the beginning of the pandemic, several vaccines have been developed that have demonstrated a significant response in the general population in terms of immunogenicity and efficacy^{3,4}. This has been developed to hopefully revolutionize the fight against the COVID-19 pandemic^{5,6}.

It is well known from prior studies that vaccine immunogenicity in other viruses, such as influenza, is diminished in SOT recipients due to immunosuppressive medications⁷, as compared to general population. Thus, there have been several attempts to improve vaccine efficacy and/or immunogenicity in this special population, such as use of high dose vaccines⁸ and boosted doses⁹.

Even though a high efficacy of COVID-19 vaccines has been documented in the general population, there is some concern of low immunogenicity among SOT recipients of the SARS-CoV-2 vaccines¹⁰. At the same time, several reports have already documented breakthrough infection after vaccination in SOT recipients¹¹. Thus, we need to develop a better way to protect this vulnerable population with an efficient vaccine strategy.

Already, there are several reports of increased immunogenicity with additional dosing of vaccination¹². Randomized controlled trial comparing placebo vs. other mRNA vaccine as a booster dose study showed some benefit¹³. However, as of now, there is no comparison study between mRNA and adenovirus vector vaccine. This time, we are conducting single center randomized controlled trial comparing mRNA vs. Adenovirus vector vaccine as a third dose after completion of two doses of mRNA vaccine in solid organ transplant recipients.

3) Inclusion and Exclusion Criteria*

Inclusion Criteria:

- *Patients 18 years of age and older*
- *Patients who had received a solid organ (kidney, liver, lung, heart, and pancreas) transplant patient from living or deceased donors.*
- *Patients with active graft with at least one immunosuppressive medication*
- *Completed two doses of BNT162b2 vaccination at least 28 days ago*

Exclusion Criteria:

- *Patient with non-active graft*
- *Any significant side effect with previous COVID-19 vaccination*
- *Within 28 days of BNT162b2 vaccine completion*
- *Already received more than and equal to three doses of COVID-19 vaccination*
- *Previously received COVID-19 vaccine other than BNT162b2 vaccine*
- *Previously received monoclonal Antibody treatment that are specifically directed against the spike protein for SARS-CoV-2 such as Mab, Bamlanivimab, etesevimab, Casirivimab, imdevimab, Sotrovimab and/or any combination.*

IRB Study Number: 20210641
 Version #4, Date: October 26, 2021

- *Thrombocytopenia (listed as a medical diagnosis or less than 50,000 per microliter 30 days prior vaccination)*
- *History of Capillary Leak Syndrome*
- *Adults unable to consent*
- *Individuals who are not yet adults (younger than 18 year old)*
- *Vulnerable patients (prisoners)*
- *Pregnant women*

4) Evaluation

Evaluation will be conducted as below schedule.

Procedures	Screening	Enrollment/Baseline Visit 1, Day 1	Phone Call Visit 2 48-96 hours	Phone Call Visit 3 6-8 days	Study Visit 4 Day 28 +/- 7 day	Study Visit 5 Month 6 (+/- 7 days)	Study Visit for Sub study only At Month 6 (+/- 30 days)
Informed consent	X	X					
Demographics	X	X					
Medical history	X	X					
Randomization	X	X					
Blood sample collection		X			X		X*
Vaccine Administration		X					
Symptom checker		X	X	X	X		
Phone call follow up			X	X	X	X	

* 50 optional participants only

Blood samples will be obtained from all patients at the time of enrollment (Day 1) and day 28 to test IgG and IgM against SARS-CoV-2 spike protein.

IRB Study Number: 20210641
Version #4, Date: October 26, 2021

At month 6, 50 optional patients will join to participate in the sub-study which will consist of blood sample collection to measure long term immunogenicity (IgG and IgM).

5) Sample Size calculation

The primary outcome of this study is IgG positivity after 28 (21-35) days of the booster dose of the either vaccine. This IgG should be antibody against spike protein, and reported as RBD, measured by [name] lab. We put alfa of 0.05 and beta of 0.2. The IgG positivity in JNJ-78436735 should be assumed as 80% and BNT162b2 as 60%.

6) Number of Subjects*

The Number needed in this study should be 93 per one arm, which is 186 in total. We assume 5-10% follow-up lost so we are going to enroll 200 patients in total.

For sub study to measure long term immunogenicity, we will enroll 50 patients among 200 participants.

The participants will be contacted via phone call in 6 months for monitoring.

7) Description of the study

This is the patient-blinded randomized controlled trial. To monitor patient reporting side effect properly, we are going to conduct the patient-blinded. Study team member will be aware after randomization, at the time of giving vaccination. This is not observer blinded. Also, to minimize bias, [name] lab members will not be notified which vaccine each participant receives. Randomization will be conducted via excel by [name]. Adult transplant recipients will be recruited from outpatient clinics. Transplant patients will be randomized in a 1:1 ratio.

8) Randomization of vaccine

A randomization schedule will be created using Microsoft Excel. [name] will randomly select 100 numbers out of 200 using excel. The selected number patients will receive JNJ-78436735 vaccine. The rest will receive BNT162b2 vaccine. Those randomized result will put into 200 envelopes. On top of each envelope, only study ID, from 001 to 200, will be written. The envelope will be filed in each patient's research chart. Charts will be located at the research office located at the Elliot Building. Only the study team will have access to the building.

After obtaining consent, study team member, other than [name], will open the envelope to identify which vaccine to give. Each participant should be randomized and will receive one time dosing of either JNJ-78436735 or BNT162b2. After vaccination, those patients will need to stay Miami Transplant Institute outpatient clinic waiting area for 15minutes (+/- 2 minutes) to be monitored.

9) Discontinuation of patients:

- Patients may be discontinued under the following circumstances:
- A patient desire for discontinuation for any reason

IRB Study Number: 20210641
Version #4, Date: October 26, 2021

- Lost to follow up (every effort must be made to contact the patient)
- Death
- An Investigator's opinion that continuing the patient in the study is not appropriate

10) Study Timelines*

After consent is obtained, the blood draw for all patients will be done at the outpatient clinic phlebotomy room. After that, the participants will receive either vaccine. After vaccination, those patients will stay in the clinic for 15mins and if they have any symptoms, those patients will notify the research team. In the event of any severe reaction, the principal investigator will be notified immediately. Medical intervention will be address based on each case.

On visit 2, 48-96 hours after administration of the vaccine, the research team will call the patient to collect the side effect information. Again, visit 3, 6-8 days after enrollment, the research team will call the patient to collect side effect information. The participants will be back to the Miami Transplant Institute outpatient clinic in 28 (21-35) days from enrollment for follow-up blood collection. Upon follow up blood collection, the study team will ask the patient if they develop any symptoms after booster dosing.

We will also collect the blood test at 6 months (20-28 weeks) time period for those who are enrolled in the sub-study (50 patients will be enrolled)

11) Study Endpoints*

Primary endpoint is the anti-spike protein of SARS-CoV-2 virus IgG positive rate in one month after vaccination. Secondary endpoint includes the incidence rate of COVID-19 and the severity of COVID-19.

Safety endpoints includes side effect (i.e. pain at injection site, size of indwelling, fever, fatigue, and joint pain) at day 2 and 7 after vaccination. We also follow up to 6 months for any symptoms. This could also be gathered from the Jackson Health System medical record.

12) Procedures Involved*

This is a single center single blinded (patient blinded) randomized controlled trial comparing BNT162b2 and JNJ-78436735vaccine as a third dose after completion of two doses of BNT162b2 vaccine in Solid Organ Transplant Recipients.

IRB Study Number: 20210641
Version #4, Date: October 26, 2021

Once informed consent is obtained, 10 ml of blood from the participants will be obtained at day 0 and day 28(21-35) to monitor IgG and IgM against SARS-CoV-2 spike protein. Then, a Jackson transplant nurse and/or medical assistant will intramuscularly inject either vaccine to the participants. The source of clinical information will be collected through Jackson Health System electronical medical record.

Blood test will be analyzed [name] lab in University of Miami.

As an optional sub study for 50 participants, we will collect 10 ml of blood again at 6months (20-28 weeks) time to monitor IgG and IgM.

After vaccination, those patients will need to stay Miami Transplant Institute outpatient clinic waiting area for 15minutes (+/- 2 minutes) to be monitored.

Unblinding Process:

The vaccine given at the time of enrollment will be unblinded upon patient's request at Day 28. However, if an emergency, the vaccine will be unblinded immediately for the patient.

A potential early unblinding event could occur if the patient's healthcare provider, including Jackson, provides the vaccine records from Florida Shot.

However, the early unblinding event should only affect the study secondary outcomes and will not affect primary outcome, i.e. serology data.

13) Data and Specimen Banking*

Blood specimen will be stored in [name] lab for 5 years. For sub-study, we will also obtain PBMC and this should also be stored in 5 years. Only the research team member will have an access to those specimen.

For clinical data, we will use a unique ID for each patient that does not include or derive from any identifiers. Miami Transplant Institute will retain the key to these IDs subject to local IRB review.

14) Data Management*

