The results of this trial have the potential for immediate knowledge translation and could lead to early and tangible benefits for transplant patients. If our hypothesis is correct and the novel booster vaccine strategy is safe and effective, it could even be implemented for transplant patients. In addition, the results could signal a paradigm shift for vaccination strategies in other populations of immunocompromised patients and lay the groundwork for future similar studies in these groups. Since this will be the largest yet reported sample size to assess this, the results will alleviate fears among some transplant physicians and improve vaccine uptake.

18) Sharing of Results with Subjects*

The laboratory result will be requested directly to the principal investigator. The results will be shared with the patient at the end of the study period.

19) Setting

- *Research will be done at the following locations:*

IRB Study Number: 20210641
Version #4, Date: October 26, 2021

- 1. *MTI Highland Professional building (Clinic) [name]*
- 2. *Jackson Memorial Hospital [name]*

20) Resources Available

This study will be overseen by Doctor [name], [name], and [name]. They are physicians managing the care of solid organ transplant patients at the Miami Transplant Institute.

The research office consists of five research coordinators.

All of them have more than three years' experience conducting transplant clinical studies. Besides the extended experience, coordinators attend Research Compliance and Quality Assurance training frequently.

21) Recruitment Methods

Principal Investigator and/or co-investigators will review medical records to assess if subject can be consented. Assessment will be done during regular clinic evaluation.

Transplant care provider will refer those patients during their clinical visits and notify the investigators. Investigators will evaluate their patients. If patient is a good candidate, then they discuss the study purpose, procedures, benefits and risks.

If patient agrees, an informed consent form will be signed.

Bilingual staff will approach to our Spanish-speaking patients to inform patients about the study.

Flyer will be posted in the MTI clinics as well as that, all MTI transplant physicians will be aware of this study prior to initiation.

22) Confidentiality

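### Allocation concealment is intended but not assured: envelopes lie in charts that the recruiting team can reach, and the list maker is not kept out of recruitment

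*Combined protocol and SAP*

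**What the plan says.** Section 8 (Randomization of vaccine) describes one list. A single person, whose name is masked, "will randomly select 100 numbers out of 200 using excel"; those numbers receive JNJ-78436735 and the rest BNT162b2. The results go into 200 envelopes: "On top of each envelope, only study ID, from 001 to 200, will be written". On custody it says: "The envelope will be filed in each patient's research chart". The charts are kept in a research office, and the only access rule is "Only the study team will have access to the building".

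On opening, Section 8 says that after consent a "study team member, other than [name], will open the envelope". Section 7 adds the intended timing of disclosure: "Study team member will be aware after randomization, at the time of giving vaccination". Section 7 also says that the laboratory is not told the arm.

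On recruitment, Section 21 says "Principal Investigator and/or co-investigators will review medical records to assess if subject can be consented", and leaves it to the investigators to judge who is a good candidate. Section 24 has the study team approach patients at their clinic visits.

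**The concern.** Concealment must hold during three steps: judging eligibility, obtaining consent and assigning the study ID. Someone who knows, or can find out, the next assignment can defer one patient and bring another forward. The arms then differ before anyone is vaccinated.

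Section 8 guards a later step. It says who may open an envelope, but not who may know its content beforehand. The people who can reach the charts are the people who recruit. The one person certain to have had the full list is not kept out of eligibility review, consent or ID assignment.

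The primary endpoint is the IgG positive rate at about one month, and the statistical text in Section 14 compares the arms with an unadjusted chi-square test. That test cannot correct an imbalance created at entry. Laboratory masking keeps the measurement honest but has no effect on who is in each arm.

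**Working it through.** **Step 1. What the plan secures and what it leaves open.**

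| Safeguard | In the plan? |
|---|---|
| Envelope shows only the study ID | Yes, Section 8 |
| Envelope opened after consent | Yes, Section 8 |
| Team learns the arm only after randomization | Intended, Section 7 |
| Envelopes sealed and opaque | Not stated |
| Envelopes held away from recruiters | No: in research charts that the team can reach |
| IDs assigned in ascending order after consent and confirmed eligibility | Not stated; the schedule in Section 4 marks randomization at both Screening and Day 1 |
| Excel list restricted to its maker | Not stated |
| List maker kept out of eligibility review, consent and ID assignment | Not stated; the one restriction concerns opening |
| Log of openings | Not stated |

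The log matters for a further reason. Section 14 requires a case report form for patients who received any study treatment, and analyses immunogenicity only in those vaccinated who returned for serum. A patient whose envelope was opened but who was not vaccinated need not appear in either.

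**Step 2. The plan's own figure.** No number in the plan is disputed here; 93 per arm is used below, so I reproduced it. With 70% against 50% (Section 14), two-sided alpha 0.05 and power 80%:

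n = [1.96·√(2·0.6·0.4) + 0.8416·√(0.7·0.3 + 0.5·0.5)]² / 0.2² = 93.0, so 93 per arm.

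Section 5 gives 80% against 60%, which leads to 82 by the same formula. That discrepancy is a separate matter. The planned difference is 20 points either way.

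**Step 3. Is the draw itself guessable?** For one list of 100 and 100, a recruiter who knows only past allocations and always guesses the arm with more places left is expected to be right

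100 + 2¹⁹⁹/C(200,100) − 0.5 = 100 + 8.87 − 0.5 = 108.4 times in 200, or 54%.

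This is little better than a coin toss, so the draw can stay. Someone with the list, or able to read the envelopes, knows all 200. The weakness is access.

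**Step 4. Size of a possible bias.** The inputs are assumptions, not figures from the plan: equal vaccines, 100 per arm, half of the patients with a high chance of IgG positivity (75%) and half with a low one (45%), so 60% overall. If k low-chance patients in one arm are exchanged for k high-chance patients in the other, the false difference is 2·k·(high − low)/100.

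- k = 5: 0.55·0.75 + 0.45·0.45 = 61.5%, against 0.45·0.75 + 0.55·0.45 = 58.5%; 3 points.
- k = 10: 0.60·0.75 + 0.40·0.45 = 63%, against 0.40·0.75 + 0.60·0.45 = 57%; 6 points.

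The effect on the two-sided false-positive rate at 93 per arm is Φ[(d − 1.96·SE₀)/SE₁] + Φ[(−d − 1.96·SE₀)/SE₁]. Here d is the false difference, SE₀ = √(2·0.6·0.4/93) = 0.0718, and SE₁ is the unpooled standard error at rates 0.6 ± d/2. The gap between the two kinds of patient is unknown, so a range is shown:

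| Gap (chances) | k = 5: false difference, false-positive rate | k = 10: false difference, false-positive rate |
|---|---|---|
| 10 points (65% / 55%) | 1 point, 5% | 2 points, 6% |
| 30 points (75% / 45%) | 3 points, 7% | 6 points, 13% |
| 50 points (85% / 35%) | 5 points, 11% | 10 points, 28% |

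Five exchanges put 10 of 200 patients in an arm other than the one the draw would have given; ten exchanges put 20 there.

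**The case against.** The best answer is that the plan does intend concealment. Envelopes show only an ID and are opened after consent, and the team is meant to learn the arm at vaccination. Access to an office is not access to what is inside an envelope. All of this stands. A reader might infer that allocation is simply not concealed from recruiters; the documents do not support that. For anyone without the list, exposure depends on sealing, opacity and the timing of ID assignment, and the plan is silent on these.

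Second, names are masked. That the person barred from opening is the one who drew the list is the natural reading but cannot be confirmed, and nothing says that this person recruits. This also stands. On the other reading, however, the list maker has no stated restriction at all.

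Third, the illustration needs 10 or 20 misplaced patients and recruiters who can tell likely responders apart. That is fair. A reader might cite the Background on weak vaccine response under immunosuppression as proof that they can. But that text compares transplant recipients with the general population, and every participant here takes at least one immunosuppressant. It does not show who responds within this population.

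Finally, a reader might object to staff seeing the arm in the chart during follow-up. Section 7 openly says that the trial is not observer blinded, so this is the stated design and not a failure of concealment.

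**Conclusion.** The point holds as a gap in safeguards. The plan states a custody rule and a separation rule, but together they leave eligibility review, consent and ID assignment unguarded. Nothing in the documents shows that anyone misused, or would misuse, the access. It would also go too far to say that randomization no longer protects the comparison.

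The size cannot be derived from the documents. Over the assumed gaps of 10 to 50 points, 5 or 10 exchanges give false differences of 1 to 10 points and false-positive rates of about 5% to 28%. The middle case gives 3 or 6 points and 7% or 13%. These rest on equal vaccines, a 60% mean rate, an even mix of high- and low-chance patients and deliberate steering. The planned analysis could not undo such a bias, and prevention is cheap, so the change is worth making. It does not affect the sample size, the arms or the analysis.

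**What to change.** Amend Section 8:

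1. The person who generates the Excel list takes no part in eligibility review, consent or ID assignment, and only that person can open the list.
2. Instead of filing envelopes in the research charts, use sequentially numbered, sealed, opaque envelopes held by the list maker or by another existing staff member who does not recruit for this trial.
3. Assign IDs in strict ascending order after consent and confirmed eligibility, and release only that one envelope. Log the ID, date, time and opener, including patients who are randomized but not vaccinated. Bring the randomization row of the Section 4 schedule into line.

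The 100-of-200 draw can stay. The cost is some wording, a log sheet and one team member's recruiting role. That last cost is real: Section 24 has all coordinators approaching Spanish-speaking patients, and Section 21 has the investigators assessing candidates, so the plan identifies nobody in either group who does not recruit. The unblinding rules in Section 12 need not change, because the team knows the arm once the envelope has been opened.

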1.1.1 Data Collection and Management Responsibilities

Data collection is the responsibility of the clinical trial staff at the site under the supervision of the Principal Investigator. The Principal Investigator is responsible for ensuring the accuracy, completeness, legibility, and timeliness of the data reported.

All source documents should be completed in a neat, legible manner to ensure accurate interpretation of data.

IRB Study Number: 20210641
Version #4, Date: October 26, 2021

Data for electronic CRFs will be entered into Velos. A CRF is required for every patient who received any amount of study treatment. The investigator will ensure that the CRF's are accurate, complete, legible and timely. Data recorded in the electronic case report form (eCRF) derived from source documents should be consistent with the data recorded on the source documents.

Clinical data (including adverse events (AEs), concomitant medications, and expected adverse reactions data) and clinical laboratory data will be entered into Velos, a HIPAA AND 21 CFR Part 11-compliant data capture system provided by the University of Miami. The data system includes password protection and internal quality checks, such as automatic range checks, to identify data that appear inconsistent, incomplete, or inaccurate. Clinical data will be entered directly from the source documents.

Study Records Retention

All records and documents relating to research studies and participants must be kept confidential to the extent permitted by law; however, records and documents shall be available in a timely manner to the University authorized employees or other agents authorized by the University including IRB members and HSRO staff and appropriate governmental agencies including but not limited to DHHS, OHRP and the FDA.

Although principal investigators are responsible for the creation and maintenance of research records and documents, such records and documents (including data collected pursuant to research) are the property of the University. Until the temporal requirements for record/document retention are met, investigators or others may not remove or destroy research records or documents (or copies of such records or documents) without written permission from the Vice Provost of Research. This permission requirement extends to investigators leaving the University even if they plan to continue the research at another institution.

The sample size was based on previous studies, which had indicated a response rate of approximately 50% and 70% to each vaccine.

Therefore, for an alpha of 0.05 and a power of 80%, a sample size of 93 evaluable patients in each study group should be required. As we assume 10% of the patients will not be back, we have that margin and going to enroll 200 patients in total. The immunogenicity analysis will be only performed in those who received a vaccine dose and returned for follow-up serum (per-protocol population). The safety analysis will be performed in all patients who received the study vaccine regardless of whether they returned for follow-up serum. Demographics will be analyzed using descriptive statistics. Differences in vaccine response rates between the 2 arms will be compared using χ^2 test. Pre- and post-vaccination titers will be compared using Wilcoxon rank-sum test. Univariate analyses will be performed to determine significant factors affecting seroconversion using χ^2 test for categorical variables and Mann-Whitney U test for continuous variables. We will develop multivariate model to determine the factor of positive IgG post booster dosing. For multivariate analysis, a model should be developed using variables that had a P value < 0.2 on univariate analysis. Multivariate analysis will be performed using

IRB Study Number: 20210641
Version #4, Date: October 26, 2021

binary logistic regression. Statistical significance was defined as a P value < 0.05. Statistical analysis will be performed using IBM SPSS version 26.0.

15) Provisions to Monitor the Data to Ensure the Safety of Subjects*

Study Auditing and Monitoring

This study will be monitored (as applicable) and may be audited according to the University of Miami requirements. See also

<http://research.med.miami.edu/clinical-research/crors/monitoring>

Clinical Research Operations & Regulatory Support CRORS will provide internal study monitoring compliance. Following the monitoring plan, the monitors will verify that the clinical trial is conducted and data are generated and biological specimens are collected, documented (recorded), and reported in compliance with the protocol, International Conference on Harmonization Good Clinical Practice (ICH GCP), and applicable regulatory requirements.

Trial Monitoring, Auditing, and Inspecting

The investigator will permit trial-related monitoring, quality audits, and inspections by, government regulatory authorities, of all trial-related documents (e.g., source documents, regulatory documents, data collection instruments, case report forms). The investigator will ensure the capability for inspections of applicable trial-related facilities. The investigator will ensure that the trial monitor or any other compliance or QA reviewer is given access to all trial-related documents and trial-related facilities.

Participation as an investigator in this trial implies the acceptance of potential inspection by government regulatory authorities.

Quality Assurance and Quality Control

In addition to the Clinical Monitoring component of this protocol, Quality Assurance (QA) will be implemented to assess compliance with GCP and applicable regulatory requirements. Data or documentation audited shall be assessed for compliance to the protocol, accuracy in relation to source documents and compliance to applicable regulations.

Publication and Data Sharing

All information provided regarding the trial, as well as all information collected/documentated during the course of the trial, will be regarded as confidential. The financial disclosure information will be completed prior to trial participation from all PIs and Sub-Investigators who are involved in the trial and named on the FDA 1572 form.

The Sponsor-Investigator will register the trial on www.clinicaltrials.gov. In addition, Sponsor-Investigator will publish the results of the trial.

IRB Study Number: 20210641
Version #4, Date: October 26, 2021

16) Risks to Subjects*

COVID-19 vaccination itself is routine practice at our institution however this study includes additional dosing. The major risk would be immediate local and systemic reactions. The third dose is not well assessed yet even in general population so difficult to foresee. However, given immunosuppressive state of the patients, these side effect, which is due to immune reaction, should be low.

RISK OF BLOOD DRAW

Risks and discomforts associated with having a needle placed in your arm for blood sampling include pain, bruising or bleeding at the puncture site, temporary light-headedness, and in rare cases, fainting or site infection. If faintness is felt, you should lie down as soon as possible to avoid possible injury caused by falling and tell study staff.

WHAT ARE THE RISKS OF THE JANSSEN COVID-19 VACCINE?

Side effects that have been reported with the Janssen COVID-19 Vaccine include:

- Injection site reactions: pain, redness of the skin and swelling.
- General side effects: headache, feeling very tired, muscle aches, nausea, and fever.

There is a remote chance that the Janssen COVID-19 Vaccine could cause a severe allergic reaction. A severe allergic reaction would usually occur within a few minutes to one hour after getting a dose of the Janssen COVID-19 Vaccine. For this reason, your vaccination provider may ask you to stay at the place where you received your vaccine for monitoring after vaccination. Signs of a severe allergic reaction can include:

- Difficulty breathing,
- Swelling of your face and throat,
- A fast heartbeat,
- A bad rash all over your body,
- Dizziness and weakness.

These may not be all the possible side effects of the Janssen COVID-19 Vaccine. Serious and unexpected effects may occur. The Janssen COVID-19 Vaccine is still being studied in clinical trials.

WHAT ARE THE RISKS OF THE PFIZER-BIONTECH COVID-19 VACCINE?

There is a remote chance that the Pfizer-BioNTech COVID-19 Vaccine could cause a severe allergic reaction. A severe allergic reaction would usually occur within a few minutes to one hour after getting a dose of the Pfizer-BioNTech COVID-19 Vaccine. For this reason, your vaccination provider may ask you to stay at the place where you received your vaccine for monitoring after vaccination. Signs of a severe allergic reaction can include:

IRB Study Number: 20210641
Version #4, Date: October 26, 2021

- Difficulty breathing
- Swelling of your face and throat
- A fast heartbeat
- A bad rash all over your body
- Dizziness and weakness

Side effects that have been reported with the Pfizer-BioNTech COVID-19 Vaccine include:

- severe allergic reactions
- non-severe allergic reactions such as rash, itching, hives, or swelling of the face
- injection site pain
- tiredness
- headache
- muscle pain
- chills
- joint pain
- fever
- injection site swelling
- injection site redness
- nausea
- feeling unwell
- swollen lymph nodes (lymphadenopathy)
-
- diarrhea
- vomiting
- arm pain

17) Potential Benefits to Subjects*

The results of this trial have the potential for immediate knowledge translation and could lead to early and tangible benefits for transplant patients. If our hypothesis is correct and the novel booster vaccine strategy is safe and effective, it could even be implemented for transplant patients. In addition, the results could signal a paradigm shift for vaccination strategies in other populations of immunocompromised patients and lay the groundwork for future similar studies in these groups. Since this will be the largest yet reported sample size to assess this, the results will alleviate fears among some transplant physicians and improve vaccine uptake.

18) Sharing of Results with Subjects*

The laboratory result will be requested directly to the principal investigator. The results will be shared with the patient at the end of the study period.

19) Setting

- *Research will be done at the following locations:*

IRB Study Number: 20210641
Version #4, Date: October 26, 2021

- 1. *MTI Highland Professional building (Clinic) [name]*
- 2. *Jackson Memorial Hospital [name]*

20) Resources Available

This study will be overseen by Doctor [name], [name], and [name]. They are physicians managing the care of solid organ transplant patients at the Miami Transplant Institute.

The research office consists of five research coordinators.

All of them have more than three years' experience conducting transplant clinical studies. Besides the extended experience, coordinators attend Research Compliance and Quality Assurance training frequently.

21) Recruitment Methods

Principal Investigator and/or co-investigators will review medical records to assess if subject can be consented. Assessment will be done during regular clinic evaluation.

Transplant care provider will refer those patients during their clinical visits and notify the investigators. Investigators will evaluate their patients. If patient is a good candidate, then they discuss the study purpose, procedures, benefits and risks.

If patient agrees, an informed consent form will be signed.

Bilingual staff will approach to our Spanish-speaking patients to inform patients about the study.

Flyer will be posted in the MTI clinics as well as that, all MTI transplant physicians will be aware of this study prior to initiation.

22) Confidentiality

Data will be stored in an electronic password protected database. Patient will be identified with a study number and it will be linked to the subject's JHS MRN. This will be kept in a separate location and locked in the research office.

IRB Study Number: 20210641
Version #4, Date: October 26, 2021

Choose the statements below that are applicable to this research:

26(a). Will the research collect protected health information or personally identifiable information from the EMR or from subjects at UHealth and/or JHS?

Yes (If checked go to 26(b))
 No (If checked, go to Section 27)

26(b). Check the box next to the correct statement below

Research Subjects will sign a HIPAA Authorization before the research will collect this data.
 Research Subjects will not sign a HIPAA Authorization for this data collection and the research is requesting a waiver of HIPAA authorization from the IRB. *(If checked, complete Section 17 below)*

26(c). How will the research store the data? *(See Section 26(e) below)*

On a University of Miami electronic device (e.g. encrypted, password-protected computer)
 On a cloud-based storage system that is approved by the University of Miami
 On the secured JHS SharePoint environment *(required for protected health information or identifiable information collected from JHS records without a waiver of authorization from an IRB.)*
 Other, specify: Click here to enter text.

26(d) Select one of the following:

The Principal Investigator (and/or Study Team members) will record (e.g. write down, abstract) data acquired in a manner that does not include any indirect or direct identifiers (listed in the instructions for Section 26 of this protocol), and the recorded data will not be linked to the individual's identity.

OR

The Principal investigator (and/or Study Team members) will record (e.g. write down, abstract) the data collected in a manner that does not include any direct identifiers (see list in the instructions for Section 26 of this protocol) of any subject. Instead, the Principal Investigator and/or Study Team members shall will assign a code (that is not derived in whole or in part from any direct or indirect identifiers of the individual) to each study subject and link the code to the study subject's identity. The link to each subject's identity and/ or other identifiable information will be maintained on a document separate from the research data.

26(e) Additional requirement for Jackson Health System Data:

Not-applicable, no data will be acquired from JHS under a waiver of authorization.
 JHS data, including Protected Health Information (PHI) and/or Personally Identifiable Information (PII), acquired from JHS for this research under a waiver of authorization shall only be stored on the secured JHS SharePoint environment made available by JHS. I and

IRB Study Number: 20210641
Version #4, Date: October 26, 2021

the Study Team members shall not copy or store the JHS sourced personally identifiable information (PII), including protected health information (PHI) data to any other system, including any systems maintained or provided by the University of Miami. I and the Study Team shall only copy or transfer JHS-sourced data that has been properly de-identified in accordance with all requirements contained in the HIPAA Rules by removing all of the identifiers listed in the instructions for Section 26 of this protocol.

27. Biospecimens

- Not applicable. No biospecimens will be collected
- Bio-Specimens obtained for this research will be stored without any direct or indirect identifiers.*
- Bio-Specimens obtained for this research will be stored in a de-identified coded manner.*
- When required to transport data or bio-specimens for this research, the research team will transport the data and bio-specimens in a de-identified (or anonymous) manner with a link to the individual subject's identity maintain separately from the data and/or bio-specimen.

23) Compensation for Research-Related Injury

If the patient gets sick because of being in this study, treatment will be available in most cases. The patient's insurance may or may not pay for these costs. If the patient have insurance, or if the patient's insurance company refuses to pay, patient will need to pay.

24) Consent Process

Informed consent will be obtained from subjects who are willing to participate in the study. The study team will approach to potential subjects during clinical visits. Clinical visits are done at Highland Professional Building. Participants will be given sufficient time to consider taking part in the study. They may take home a consent for review. Due to our population, Spanish speaking subjects will also be enrolled in the study. All research coordinators are bilingual and they will approach to these subjects. Prior consenting, all ICFs will be translated by the certified translator and approval will be obtained from the IRB.

